1.2.2 Long-term Follow-up

The long-term follow-up period will start after the EOCT/end of additional cycles (EOAC)/early withdrawal (EW) Visit.

Tumour assessments will be performed every 3 months (± 2 weeks) until whichever occurs first: documented disease progression (radiological or clinical as per investigator's judgement), 2 years after the EOCT/EOAC/EW Visit, withdrawal of consent, lost to follow-up or death.

Safety assessments and the subject's status will be assessed every 3 months (± 2 weeks) until whichever occurs first: 2 years after the EOCT/EOAC/EW Visit, withdrawal of consent, lost to follow-up or death.

After the long-term follow-up period is completed i.e. 2 years after the EOCT/EOAC/EW Visit, all subjects will be invited to participate in a safety surveillance study, as part of a separate study protocol. All subjects will be asked to sign a new informed consent form to enter this study. The purpose of the safety surveillance study is to monitor any long-term effects of ^{177}Lu -OPS201 up to 5 years from the first dose of ^{177}Lu -OPS201.

Extra visits, examinations, tests and interventions can be performed at any time if clinically indicated, as judged by the investigator.

1.2.3 *Additional Optional Cycles Part B*

If a subject tolerates the treatment well and shows clinical benefit (e.g. CR, PR, or SD) up to two additional cycles at a radioactivity dose adjusted based on dosimetry results can be administered to this subject provided limiting organ absorbed dose levels have not been exceeded. Two cycles would consist of ^{177}Lu -OPS201 administration every 8 weeks (+2 weeks, or plus up to 4 weeks in case of AEs which are not adequately recovered) with administration of the same peptide mass dose as Cycle 1. In this case, subjects will have the same assessments as during the core treatment cycles and up to EOAC or early withdrawal except for exploratory biomarkers **CCI**. Dosimetry will thus be performed after each additional cycle to prevent exceeding limiting organ absorbed doses. For these subjects, an EOAC visit will be done 8 weeks (± 5 days) after the last ^{177}Lu -OPS201 dose administration. In this case, the 2-year long-term follow-up will start at the EOAC (instead of EOCT).

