3.2.1.2 Adverse events

All AEs will be recorded and graded by investigators using the NCI CTCAE classification v5.0 and will be coded using the Medical Dictionary for Regulatory Activities (MedDRA) Version 21.1 or higher and will be classified by MedDRA preferred term and system organ class.

Listings will be presented and sorted by study part, cohort (part B only), radioactivity level adapted or not (part B only), subject number, start time of AEs, primary system organ class, preferred term and verbatim text for all adverse events recorded during the study.

Listings of all adverse events, serious adverse events (SAE), adverse events leading to withdrawal, adverse events leading to dose reduction, adverse events leading to dose interruption, adverse events leading to dose delayed, adverse events with CTCAE Grade 3,4 and 5 and listings of deaths will also be presented.

Treatment Emergent Adverse Events (TEAE) will be flagged (*) in the adverse events listing and will be summarised.

A TEAE is defined as any adverse event that occurs up to 6 months (180 days) post last dose if:

- (1) it was not present prior to receiving the first dose of IRPP (or OPS301 if applicable), taking into account the time of administration and the time of AE, or
- (2) it was present prior to receiving the first dose of IRPP (or OPS301 if applicable) but the intensity/grade increased during the active phase of the study, taking into account the time of administration and the time of AE, or
- (3) it was present prior to receiving the first dose of IRPP (or OPS301 if applicable), the intensity/grade is the same but the causality changed to “related” during the active phase of the study, taking into account the time of administration and the time of AE.

Phase of the study will be defined into 3 time periods:

- period 1: treatment intake up to 56 days/8 weeks (corresponding to 8 half-lives of the ¹⁷⁷Lutetium rounded to the upper number of weeks, 162 hours * 8 + 2 days) after last dose
- period 2: 57 days up to 6 months post last dose
- period 3: after 6 months of last dose until 2-year follow-up period /death or lost to follow-up

An overall summary table (by period 1, 2 and 1+2) of all treatment emergent adverse events will be presented by study part, cohort (part B only) and overall using the Safety Analysis Set. This table will be also repeated for period 3.

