A listing of dates of assessments (relative day), including EOCT, EOAC (part B only) and End of Long-term Follow-up (EOLTFU) dates and their study exposure will be presented by subject for each study part, cohort (part B only) and radioactivity level adapted or not (part B only). Subject disposition information will be presented using the eligible subject set.

A summary table will be presented for each subject population presenting the number of subjects in each study part and cohort (part B only) at each assessment and identifying the number of subjects who withdrew over time. The reasons for exclusions from each of the populations will be listed and tabulated.

A listing of any deviations due to COVID-19 will be generated separately and a table summarizing Deviations due to COVID-19 will be produced.

The number of patients exposed to COVID-19 as well as impacted or infected (see definition below) will also be presented.

The number of visits impacted due to COVID-19 with the reasons will be summarized to assess the impact of COVID-19

A summary table will present the number of subjects who received study treatment, extent of subject exposure in the study and the study drug exposure for each study part and cohort (part B only).

The definition of the extent of subject exposure is the time interval between the first informed consent signed to the EOCT, EOAC (Part B) or EW visit completed (c.f. in [Appendix 1: Derived Data](#)). The definition of Study drug exposure (days) is the time interval between last drug intake - date of first drug intake +1 (c.f. in [Appendix 1: Derived Data](#)).

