times are available, the time will be calculated as (start date/time – last administration date/time) and presented in days hh:mm. If at least one time is missing and if the time to onset is greater than 24 hours then it will be calculated as (start date - last administration date)+1 and presented in days. If the start date and the associated information do not allow to state about the last dose received (partial start date or start at administration day without knowing if it started before or after the drug intake), all the possible time since last dose will be presented [i.e.: if a subject received a daily administration and reported an AE at second administration day but without indication about before or after the drug intake the time since last dose will be as “2 / <1”]. If the start date is partial, the time since last dose will be presented as an superior inequality (i.e.: for an AE started in FEB2004 after the only administration performed on 31JAN2004, the time since last dose will be as “≥2” days). If the start date is missing the time since last dose will not be presented although the AE will be assigned to each dose received before its end date.

(6) Days since last dose for study drug administration or discontinued subject

The days since last dose for study drug administration will be calculated as (drug administration date/time - previous administration date/time)+1 and presented in days hh:mm. The days since last dose for discontinued subject will be calculated as (discontinued date - last administration date)+1 and presented in days.

(7) Time since initial diagnosis (months) will be calculated as (screening date - date of initial diagnosis + 1)/30.4375

(8) Time since histologically confirmed NET diagnosis (months) will be calculated as (screening date - date of histologically confirmed NET diagnosis + 1)/30.4375

(9) Time since scan of positive somatostatin receptor documentation (months) will be calculated as (screening date - date of scan of positive somatostatin receptor documentation + 1)/30.4375

(10) Time since last relapse/ time since last previous surgery for NET (months) will be calculated as (screening date - date of last relapse/surgery + 1)/30.4375

(11) Study exposure

Study exposure in days will be calculated as (last visit attended - first inform consent signed date) + 1.

(12) Duration of Study Drug Exposure

Duration (days) = (last dose or infusion date - first dose or infusion date +1)

(13) Delay in injection

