A delay in injection is defined as an injection performed more than one day after the scheduled injection date.

The number of days of delay will be positive and calculated as the difference between the actual injection date and the scheduled injection date.

(14) **Injection performed in anticipation**

An injection performed in anticipation is defined by an injection performed more than 1 day in advance compared to the scheduled date.

The number of days of anticipated injections will be positive and calculated as the difference between the scheduled injection date and the actual injection date.

(15) **Concomitant therapy duration**

If times are available, the duration of concomitant treatments/physiotherapy etc. will be calculated as (end date/time - start date/time). If at least one time is missing, the duration of concomitant treatments will be calculated as (end date - start date) +1. If the recorded end date is CONT. (for continuing) then the end date will be listed as “ongoing” and the duration will be approximated as “≥(last attended visit date – start date)+1” day(s). If the start date or the end date are partial, the duration will be presented as an inequality “≥xx” day(s) [i.e.: ≥2 where start date=31JAN2004 and end date=FEB2004 or start date=JAN2004 and end date=01FEB2004] but if both are partial or one is missing the duration will not be presented.

(16) **Study day**

Study day will be defined as ‘-1’ for the day prior to treatment and as ‘1’ for the day of treatment (i.e. day 0 does not exist).

(17) **For quantitative statistics of biological values, a standardization method will be used in order to take into account the differences between the reference ranges of the different laboratories:**

In a general way, standardised values will be assessed using the following formula:

$$X_{St.} = X_{LRef} + (X_{URef} - X_{LRef}) \frac{X - X_L}{X_U - X_L}$$

where X = measured value,

XL = lower limit value for the laboratory of the measured value,

XU = upper limit value for the laboratory of the measured value,

XLRef. = lower limit value for the laboratory chosen as a reference,

XURef. = upper limit value for the laboratory chosen as a reference,

If a standardised value is negative it will be replaced by 0.

There is no missing value for any reference value.

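### SAP Appendix 1 ends study exposure at a different visit from section 3.2.5 and adds a day to timed dosing intervals; two further derivation rules need a clearer label or definition

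*SAP*

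**What the plan says.** **Study exposure.** SAP 3.2.5 (Subject disposition) states that the "extent of subject exposure is the time interval between the first informed consent signed to the EOCT, EOAC (Part B) or EW visit completed" and refers the reader to Appendix 1. Item (11) of SAP 7.1, Appendix 1, states: "Study exposure in days will be calculated as (last visit attended - first inform consent signed date) + 1". SAP 1.2.2 continues safety follow-up until the first of "2 years after the EOCT/EOAC/EW Visit, withdrawal of consent, lost to follow-up or death". SAP 3.2.1.7 (Extent of Exposure) also summarises an overall study duration and refers to section 7.1 for it, but no visible item in 7.1 carries that name.

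**Interval between doses.** Item (6) calculates days since last dose, for each study drug administration, as ("drug administration date/time - previous administration date/time)+1 and presented in days hh:mm".

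**Drug exposure.** Item (12): "Duration (days) = (last dose or infusion date - first dose or infusion date +1". SAP 3.2.5 gives the same formula, and SAP 3.2.1.7 summarises the result as duration of exposure on the safety population. Separately, SAP 3.2.1.2 defines adverse-event period 1 as "treatment intake up to 56 days/8 weeks (corresponding to 8 half-lives of the" radionuclide, counted after the last dose.

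**Delay.** Item (13): "A delay in injection is defined as an injection performed more than one day after the scheduled injection date". The scheduled injection date is not defined. Protocol 3.1 and the visit windows in SAP 3.2.14 allow dosing at 8 weeks +2 weeks, with up to +4 weeks where toxicity has not recovered.

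**The concern.** A programmer who follows 3.2.5 and one who follows item (11) would both be complying with the SAP and would report different values for every subject who attends a follow-up visit. Under item (11) the value for such a subject would also grow between the third interim analysis and the final analysis, although treatment had already ended. Under 3.2.5 it would not.

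The other three items raise smaller questions. Item (6) departs from the convention used elsewhere in the same appendix. Item (12) applies a formula suited to continuous dosing to a product given as one infusion every 8 weeks, so a subject who stops after Cycle 1 is shown with 1 day of exposure. Item (13) could place doses that respect the protocol in the same listing as late ones.

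Exposure tables are the background against which the primary safety results are read, so the quantities should be unambiguous and should mean what their labels say.

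**Working it through.** The plan states no numerical result for these derivations, so there is no figure to reproduce. The check applies each rule to the nominal schedule.

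**Inputs**
- Consent 7 to 28 days before first dose (screening Week -4 to -1, SAP 3.2.14).
- Doses 56 days apart (Protocol 3.1).
- EOCT at Week 24, which is 168 days after first dose (SAP 3.2.14).
- EOAC 56 days after the last dose. After five cycles this is 4 × 56 + 56 = 280 days after first dose.
- Complete follow-up of 2 years, taken as 730 days (SAP 1.2.2).

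**Study exposure.** Section 3.2.5 does not write a +1. It is included in both columns so that only the end point differs.

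| Case | To EOCT/EOAC (3.2.5) | To last visit attended (item 11) | Ratio |
|---|---|---|---|
| 3 cycles, consent 28 days before | 168 + 28 + 1 = 197 | 197 + 730 = 927 | 4.7 |
| 3 cycles, consent 7 days before | 168 + 7 + 1 = 176 | 176 + 730 = 906 | 5.1 |
| 5 cycles, consent 28 days before | 280 + 28 + 1 = 309 | 309 + 730 = 1039 | 3.4 |

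The gap equals the time from EOCT/EOAC/EW to the last visit attended. It is 0 for a subject with no follow-up visit and about 730 days for a subject with complete follow-up.

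**Item (6).** Two doses exactly 56 days apart give 56 days 00:00 + 1 = 57 days 00:00. Under item (5), an adverse event starting at that same moment, measured from the first of those doses, is 56 days 00:00. Items (4), (5) and (15) all take the plain difference when times are available and add 1 only to date-only counts. The second half of item (6), days from last dose to discontinuation, is date-only, so its +1 follows that convention.

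**Item (12).** With on-time dosing, last minus first infusion + 1 is 56 × (cycles − 1) + 1. Counting a 56-day final cycle gives 56 × (cycles − 1) + 56.

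| Cycles | Item (12), days | With 56-day final cycle, days | Item (12) as share |
|---|---|---|---|
| 1 | 1 | 56 | 2% |
| 2 | 57 | 112 | 51% |
| 3 | 113 | 168 | 67% |
| 5 | 225 | 280 | 80% |

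The 56 days match the period that SAP 3.2.1.2 uses for adverse events: 8 × 162 hours = 1296 hours = 54 days, plus 2 days.

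**Item (13).** Assume that the scheduled date is the nominal Week 8 date. The ordinary +2-week window then covers offsets of 0 to 14 days, which is 15 possible days. Offsets of 2 to 14 days exceed one day, so 13 of the 15 (87%) would be called delays. If the scheduled date means something else, this count does not apply.

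**The case against.** **Items (11) and 3.2.5 may describe two quantities.** SAP 3.2.1.7 separately asks for an overall study duration, and consent to last visit fits that name. The opening of 3.2.5 also lists study exposure beside the end of long-term follow-up date. On that reading the fault is a label or a cross-reference. This is plausible, but it does not remove the problem: 3.2.5 would then refer to Appendix 1 for a derivation that is not visibly there, and item (11) would be serving two quantities with different end points. Some appendix entries are redacted, so this rests on the visible items.

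**Item (12) is not an error.** This stands. It agrees with 3.2.5, and the 56-day period in 3.2.1.2 classifies adverse events; the SAP does not use it to define exposure. SAP 3.2.1.7 also reports the number of cycles and the cumulative activity, so a 1-day value would not be read alone. What remains is that the label promises more than the formula measures.

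**Item (13) may be harmless.** This stands in part. Because the scheduled date is undefined, misclassification of in-window doses is conditional. A reader might infer that toxicity-driven delays could not be told apart from ordinary scheduling. The documents do not support that: SAP 3.2.1.2 plans a listing of adverse events leading to dose delay and a summary table of treatment-emergent events leading to dose delays.

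**The added day in item (6) is trivial.** Its effect is one day, and no planned analysis was found that uses the field to judge compliance with the dosing window. It is still inconsistent with items (4), (5) and (15).

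**Conclusion.** Two rules need correction as written. The end point of study exposure differs between SAP 3.2.5 and item (11), with a gap of up to about 730 days per subject (197 against 927 days in the main example, assuming on-time dosing, 28-day screening and complete follow-up). The timed part of item (6) overstates each dosing interval by one day.

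Two further points are secondary. Item (12) is internally consistent but, reported as duration of exposure, omits the final 8-week cycle. Item (13) lacks a definition, and would list 13 of the 15 in-window days as delays only if the scheduled date is nominal Week 8.

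A reader might infer that the appendix's exposure rules are arithmetically wrong throughout, or that the primary safety conclusions are at risk. Neither follows. The drug-exposure formula is the same in both places, adverse events are summarised as numbers and percentages of subjects, and the treatment-emergent window is set independently of these derivations. No DLT rule, efficacy estimate or sample size changes. The affected outputs are descriptive.

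**What to change.** 1. Replace item (11) with two named derivations: subject exposure (consent to EOCT/EOAC/EW, + 1) and overall study duration (consent to last visit attended, + 1). Refer SAP 3.2.5 to the first and 3.2.1.7 to the second.
2. In item (6), remove the +1 from the date/time version only. Keep it for the date-only count to discontinuation.
3. Either relabel item (12) as the first-to-last infusion interval, or report last minus first infusion + 56 days (56, 112 and 168 days for one, two and three on-time cycles), truncated at death or last contact. Use the same wording in 3.2.5 and 3.2.1.7.
4. In item (13) and the delay listing, state what the scheduled injection date is, and flag doses inside the protocol's stated window separately from those beyond it.

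The cost is wording in Appendix 1, 3.2.5 and 3.2.1.7 and minor reprogramming of derived variables. No new data are needed.

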1.3.3.3.2 Blood Biochemistry

Biochemistry parameters include sodium, potassium, chloride, calcium, glucose, creatinine, urea, albumin, total bilirubin, AST, ALT, alkaline phosphatase, GGT, C-reactive protein. Creatinine clearance will also be calculated.

The eGFR value will be calculated by the Modification of Diet in Renal Disease (MDRD) formula.

Biochemistry will be measured at the Screening Visit, at Visits 1 to 3 and optional Visits 4 and 5 (predosing, 24±1 hour (Day 2), 48±1 hour (Day 3), 72 to 96 hours (Day 4 to 5), 144 to 168 hours (Day 7 to 8) and Day 15±2 days), Follow-up Visits, the EOCT/EOAC/EW Visit and the visits in the 2-year long-term follow-up period.

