3.2.1.3 Laboratory data

A separate listing of normal ranges for SI and local laboratories units will be provided by study site laboratory, gender and age where relevant.

Laboratory data (including hematology, biochemistry, pituitary markers and urinalysis) will be listed in SI and local laboratories units and abnormal values will be flagged (High, [H], Low [L], clinically significant [C], CTCAE version 5.0 grade (G)) where applicable. Any unscheduled laboratory assessments will be flagged [U] in the listings. In addition, a listing of clinically significant abnormal values will be presented.

As multiple local laboratories are used within the study, a data normalisation method (refer to [Appendix 1: Derived Data](#), and Ref. 5, 6, 7) will be used before summarising the data. The normalized lab data values will be also included in the lab data listings together with the reference normal range limits used for the normalisation.

(a) Hematology, Biochemistry and Pituitary Markers

For hematology, biochemistry and pituitary marker parameters, the baseline will be defined as the last measurement collected prior to the first dose of study drug.

For hematology, biochemistry and pituitary marker parameters, summary statistics, by study part, cohort (part B only) and overall, will be presented at each scheduled assessment for normalised actual values and changes from baseline. For pituitary markers, all values will be displayed in a listing, however the summary tables may exclude any results if it was drawn while the subject was receiving medication that may have been deemed to impact the result.

The determination of the medications impacting the result will be based upon medical monitor review and reflected in a footnote.

Shift tables from Baseline to worst post-baseline and also, each post baseline visit. In the shift tables, the number and percentages of subjects with low, normal, or high values will be presented by study part, cohort (part B only) and overall.

For hematology and biochemistry, summary statistics by study part, cohort (part B only) and overall, will be also provided for nadir and day to nadir by cycle (time from cycle baseline to nadir during the same cycle) and on lab toxicities after start of study medication with worst CTCAE version 5.0 Grades 3 and 4 (refer to Appendix 1, Derived data).

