Shift tables from Baseline to worst CTCAE version 5.0 Grade of hemoglobin, absolute neutrophil count, and platelet count, will be presented by study part, cohort (part B only) and overall.

Hematological and biochemistry toxicities will be recorded and graded according to the CTCAE criteria, Version 5.0. The CTCAE grade (0 to 4) of hematology and biochemistry by cycle and by subject will be listed in the Section 16.2.8. Listings of the laboratory parameters in section 14.3.4 will include a listing of all CTCAE Grade 3 and 4 hematological toxicities, a listing of CTCAE Grade 3 and 4 hematological toxicities lasting 4 weeks or more, a listing of CTCAE Grade 2 hematological toxicities lasting 4 weeks or more, a listing of all CTCAE Grade 3 and 4 biochemical toxicities, a listing of CTCAE Grade 3 and 4 biochemical toxicities lasting 4 weeks or more, a listing of CTCAE Grade 2 biochemical toxicities lasting 4 weeks or more, a listing of all eGFR of < 45mL/min, a listing of eGFR of < 45mL/min lasting 4 weeks or more, a listing of out of range biochemistry parameters that could not be graded using CTCAE grade (below LLN – normal – above ULN) and a listing of biochemistry parameters that could not be graded using CTCAE grade (below LLN – normal – above ULN) lasting 4 weeks or more.

In addition, figures of absolute leucocyte count, absolute neutrophil count, absolute lymphocyte count, platelet count, hemoglobin, AST, ALT, AP, total bilirubin, creatinine, eGFR individual normalised values over time will be displayed.

(b) Urinalysis

For categorical urinalysis data (absent/trace/positive and normal/abnormal) frequency tables, by study part, cohort (part B only) and overall, will be presented at each scheduled assessment as well as the change from baseline with the following categories: improved, stable, worsened and abnormal worsening.

Shift tables from Baseline to each post baseline visit for the number and percentage of subjects with normal, abnormal clinical evaluation will be presented by study part, cohort (part B only) and overall.

For continuous urinalysis data (specific gravity, PH), summary statistics, by study part, cohort (part B only) and overall, will be presented at each scheduled assessment for actual values and changes from baseline.

3.2.1.4 *Vital signs, weight and height*

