(18) **A nadir** for a subject is defined as the lowest laboratory value during the whole treatment period (all cycles combined) among all infusions for that subject and a nadir for a cycle is defined as the lowest laboratory value in that cycle. The day to nadir in a cycle is the number of days between the nadir and the first date of study medication intake of that cycle.

(19) **Whole body absorbed dose**

$$\text{AbsorbedDose_WholeBody [Gy]} = \text{AUC}_{\text{WholeBody}} [\text{Bq.s}] \times E_{\text{beta}} / \text{Weight}_{\text{WholeBody}} [\text{kg}]$$

With $E_{\text{beta}} = 2.3664 \times 10^{-14} \text{ J.Bq}^{-1} \cdot \text{s}^{-1}$.

(20) Whole body specific absorbed dose

$$\text{Specific_AbsorbedDose_WholeBody [Gy/GBq]} = \frac{\text{AbsorbedDose_WholeBody [Gy]}}{\text{Radioactivity_administered [GBq]}}$$

(21) Amount excreted (Ae) for cold PK urine sample

$$\text{Ae [ng]} = \text{ConcentrationOPS201_urine (ng/mL)} \times \text{volume urine collected (mL)}$$

CCI

CCI

CCI

CCI

CCI

CCI

CCI

CCI

CCI

CCI

CCI

CCI

CCI

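### Blood counts and eGFR are summarised and plotted after linear rescaling to a reference laboratory with negatives set to 0, so low values can be shown far from what was measured

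*SAP*

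**What the plan says.** Haematology and biochemistry are tested at site laboratories (SAP 1.3.3.3), with about 20 sites planned (SAP 1.2.1). Because several laboratories are involved, SAP 3.2.1.3 says that a normalisation method "will be used before summarising the data. The normalized lab data values will be also included in the lab data listings".

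Appendix 1 item (17) gives its purpose: "a standardization method will be used in order to take into account the differences between the reference ranges of the different laboratories". The item maps the local lower and upper limits onto those of a reference laboratory by a straight line. It names no exempt analyte and ends: "If a standardised value is negative it will be replaced by 0".

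Two kinds of output use the result by name:

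- By-visit summary statistics for haematology, biochemistry and pituitary markers "will be presented at each scheduled assessment for normalised actual values and changes from baseline".
- Individual plots: leucocyte, neutrophil and lymphocyte counts are named first, and the list continues "platelet count, hemoglobin, AST, ALT, AP, total bilirubin, creatinine, eGFR individual normalised values over time will be displayed".

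For nadir the scale is not given. Summary statistics "will be also provided for nadir and day to nadir by cycle", and item (18) says only that a subject's nadir "is defined as the lowest laboratory value during the whole treatment period". The SAP also contains no sentence saying that CTCAE grading uses measured values.

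**The concern.** The line is fixed at two points, the lower and upper normal limits. Between them it interpolates. Below the lower limit it extrapolates, and that is where the cytopenias of interest lie. The further a count falls, the more a difference in range width matters. The zero rule shows that the SAP expects impossible negative results, and it hides them instead of preventing them.

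Safety and tolerability is the primary objective, and bone marrow and kidney are the dose-limiting organs (Protocol 11.4.6). Protocol 1.4 reports Grade 4 thrombocytopenia in four of seven subjects after the second cycle in the earlier investigator study. The plan judges these parameters against fixed absolute values: platelets 50 and (in Part A) neutrophils 1.0 ×10⁹/L, and eGFR 45 (SAP 1.3.1.3). A plot or cohort mean on the rescaled axis can put a subject on the wrong side of such a value. It can also conflict with the CTCAE tables and listings in the same report, in a direction that depends on which laboratory did the test. Several Part B cohorts may have only three to five subjects, and individual plots average nothing out.

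**Working it through.** **Formula (item 17).** X_st = LRef + (URef − LRef) × (X − L)/(U − L), then set to 0 if negative. L and U are the local limits; LRef and URef are the reference limits.

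**Inputs.** The SAP states no worked figure to reproduce and gives no laboratory ranges, so every range below is an assumption. Platelets and neutrophils are in ×10⁹/L. The platelet value 41 is the Grade 3 case (41,000/mm³) in Protocol 1.3.6, which came from compassionate use and not from this trial.

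**Platelets, one limit differing**

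| Measured | Local | Reference | Calculation | Displayed |
|---|---|---|---|---|
| 41 | 150–400 | 150–450 | 150 + 300 × (−109)/250 | 19.2 |
| 41 | 150–450 | 150–400 | 150 + 250 × (−109)/300 | 59.2 |
| 41 | 140–400 | 150–400 | 150 + 250 × (−99)/260 | 54.8 |
| 41 | 150–400 | 140–400 | 140 + 260 × (−109)/250 | 26.6 |

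Two of the four displayed values lie above 50, although the measured count is below it.

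**Platelets, full envelope** (lower limit 130–150, upper limit 350–450, for both laboratories)

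- Measured 41, minimum: local 150–350, reference 130–450 gives 130 + 320 × (−109)/200 = −44.4, displayed as 0.
- Measured 41, maximum: local 130–450, reference 150–350 gives 150 + 200 × (−89)/320 = 94.4.
- Measured 20, same two pairs: 130 + 320 × (−130)/200 = −78, displayed as 0; and 150 + 200 × (−110)/320 = 81.3.

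**Where the zero rule starts.** X_st reaches 0 at X = L − LRef × (U − L)/(URef − LRef).

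- Local 150–400, reference 140–450: 150 − 140 × 250/310 = 37.1.
- Local 150–400, reference 150–450 (one limit differing): 150 − 150 × 250/300 = 25.

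Every measured count at or below these values is displayed as 0.

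**Change from baseline, platelets 200 to 41 (true change −159).**

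- Smallest: local 130–450, reference 150–350. Baseline 150 + 200 × 70/320 = 193.8; 193.8 to 94.4 is −99.4.
- Largest: local 144–350, reference 150–450. Baseline 150 + 300 × 56/206 = 231.6; follow-up 150 + 300 × (−103)/206 = 0; change −231.6.

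**Neutrophils 0.5.** From 1.5–8.0 to 2.0–7.5: 2.0 + 5.5 × (−1.0)/6.5 = 1.15. Reverse: 1.5 + 6.5 × (−1.5)/5.5 = −0.27, displayed as 0.

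**eGFR 45.** From 60–120 to 90–120: 90 + 30 × (−15)/60 = 82.5. Reverse: 60 + 60 × (−45)/30 = −30, displayed as 0. SAP 1.3.3.3.2 says: "The eGFR value will be calculated by the Modification of Diet in Renal Disease (MDRD) formula". Rescaling that result needs a lower and an upper eGFR limit from every laboratory, and the SAP gives none.

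**Checks.** With identical local and reference limits, X_st = X. Because limits map to limits, low/normal/high shift tables do not change.

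**The case against.** The strongest reply is that the information is not lost. Listings carry each value in SI and local units with abnormality flags and CTCAE grade, and show the normalised value and reference limits beside it. Depth of cytopenia is also reported through worst-grade shift tables, Grade 3–4 listings and listings of eGFR below 45. Item (17) is confined to quantitative statistics, and nothing suggests that grading, dose-limiting toxicities or the review boards' data are rescaled. All of this stands, and it limits the reach of the point to by-visit statistics, the plots and possibly nadir.

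The magnitudes depend on assumed ranges, and the 0-to-94 span needs both limits to differ at opposite corners of the grid. That is true. However, one differing limit already moves 41 to 19 or 59, and the zero rule can then begin at 25. The eGFR example is the weakest, since the documents do not show that laboratories supply differing two-sided eGFR limits.

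The wording has some slack. In the by-visit sentence, normalised could be read as qualifying only the actual values, and item (17) describes its formula as a general approach. But SAP 3.2.1.3 applies the method before summarising, so changes are most naturally on the same scale, and no exception is stated.

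Normalisation is a deliberate choice with cited sources, and the same extrapolation affects the analytes left under it. That is conceded. The change is limited to the parameters on which marrow toxicity and renal function are read in absolute terms. Adding measured-value plots would help, but it would leave the summary statistics as they are.

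**Conclusion.** The concern holds. As written, the by-visit haematology statistics and the individual count, haemoglobin and eGFR plots show rescaled values, and low values are extrapolated and cut off at 0. Under the assumed platelet ranges, a measured 41 can be displayed as 0 to 94, and a fall of 159 as a fall of 99 to 232. The true size depends on reference ranges that the documents do not give: it is nil where ranges coincide and small where they nearly do. The point does not extend to CTCAE grades, dose-limiting toxicities, stopping rules or board decisions, for which the documents show no use of rescaled values. The scale for nadir is unstated. Because the affected outputs describe primary safety data in small cohorts, the SAP should be changed.

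**What to change.** In SAP 3.2.1.3 and Appendix 1 items (17) and (18):

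- Exclude haematology counts, haemoglobin and eGFR from the normalisation.
- Summarise and plot them as measured in SI units, including change from baseline and nadir.
- Remove the replace-by-0 rule for these parameters.
- State that CTCAE grading uses measured values. This sentence alone is a clarification.
- Leave the method unchanged for other analytes.

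The cost is SAP wording and somewhat simpler programming, since SI values are already required for the listings. The downside is that any genuine calibration difference between laboratories in these parameters is left unadjusted. No clinical rule changes.
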